7 BASELINE DATA AND FLOW CHART

7.1 Presentation of Baseline Data

The following baseline data will be presented, including data by site, asthma severity levels (mild and moderate-severe), history of allergic rhinitis or hay fever, and vaccination group: age, age-group (5-11 and 12-17 years), gender, ethnicity, race, receipt of influenza vaccine in the past 12 months, influenza season vaccinated (2018-19 and 2019-20), influenza dose received (1 or 2), and BMI.

7.2 Flow Chart

The number of enrolled participants will be presented in a flow chart by site, asthma severity levels, and vaccination group. The number of visits completed and missed will be presented along with the completeness of memory aid. A CONSORT diagram will be presented.

8 ANALYSIS OF STUDY OBJECTIVES

Descriptive analyses will be summarized for continuous variables with mean, standard deviation, median, and interquartile range. Categorical variables will be summarized with frequencies and percentages. Explanatory figures will be generated to evaluate the data distribution. Comparisons of demographic characteristics between LAIV4 and IIV4 groups will be conducted using Pearson Chi-square and Wilcoxon tests appropriately.

All analyses will be performed using R 3.6.2 (r-project.org), SAS version 9.4, or STATA version 16, or updated software from these programs.

8.1 Primary Objective

The primary objective (PO 1) of the study is to compare proportions of participants with asthma exacerbation(s) during the 42 days after LAIV4 versus IIV4 in children with asthma aged 5-17 years.

The hypothesis for this primary objective is that the proportion of participants with asthma exacerbation(s) after LAIV4 is non-inferior to the proportion of participants with asthma exacerbation(s) after IIV4 (the proportion of participants with asthma exacerbation(s) after vaccination is not higher in the LAIV4 group vs. the IIV4 group). Asthma exacerbations will be assessed from day 1 through day 43. This information is captured on the memory aid forms and recorded in the REDCap database. *Any unscheduled medical attention (e.g., healthcare provider office, emergency department visit, hospitalization) due to any acute episode of progressively worsening shortness of breath/ dyspnea, cough, wheezing, chest tightness, and/or respiratory distress OR received a new prescription for systemic corticosteroids after LAIV4 vs. IIV4 during the 42 days post-vaccination will be counted as asthma exacerbations yes (1) and asthma exacerbations no (0) otherwise, for this analysis.*

This objective will be assessed using a one-sided non-inferiority test with the alpha level set at 0.05 and non-inferiority margin of 10%. The null hypothesis is LAIV4 is inferior to IIV4 in regard to the proportion of subjects having asthma exacerbations during the 42 days post-vaccination (i.e., LAIV4 will have a higher proportion of asthma exacerbations compared to IIV4).

$$H_0: \text{LAIV4} - \text{IIV4} \geq 0.1 \text{ (10\%)}$$

The alternative hypothesis is LAIV4 is non-inferior to IIV4 in regard to the proportion of subjects having asthma exacerbations during the 42 days post-vaccination.

$$H_a: \text{LAIV4} - \text{IIV4} < 0.1 \text{ (10\%)}$$

The proportions will be compared between LAIV4 versus IIV4 using a Cochran-Mantel-Haenszel method in a stratified analysis by site to control for three sites at the one-sided alpha 0.05 level. The upper bound of 95% one-sided confidence interval for the proportion difference between two vaccine groups will be used to make this assessment and we will reject H_0 if it's less than 10%.

The proportion difference and corresponding 95% confidence interval for asthma exacerbations with or without adjusting for site will also be calculated. We may perform comparisons between LAIV4 versus IIV4 adjusting for asthma severity groups (Mild vs. Moderate-Severe) or adjusting for both site and asthma severity groups (Mild vs. Moderate-Severe) if possible.

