2.2 Study Outcome Measures

2.2.1 Primary Outcome Measure

1. Comparison of the proportion of participants experiencing an asthma exacerbation during the 42 days after LAIV4 vs. IIV4 (until day 43).

According to the 2007 *Expert Panel Report 3: Guidelines for the Diagnosis and Management of Asthma*, asthma exacerbations, "are acute or subacute episodes of progressively worsening shortness of breath, cough, wheezing, and chest tightness (or some combination of these symptoms). Exacerbations are characterized by decreases in expiratory airflow that can be documented and quantified by simple measures of lung function [spirometry or peak expiratory flow (PEF)]".²⁴ For this study, asthma exacerbation will be defined as: *any acute episode of progressively worsening shortness of breath (dyspnea), cough, wheezing, chest tightness, and/or respiratory distress during the 42 days (until day 43) after influenza vaccination for which the patient seeks unscheduled medical attention (e.g., healthcare provider office or Emergency Department visit or hospitalization) or receives a new prescription for systemic corticosteroids.*

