- The child will be randomized to the respective treatment group (LAIV4 or IIV4) using the REDCap System. The Vaccine Information Sheet (VIS) for the respective vaccine administered will be provided to parent(s) or legal guardian(s) before the vaccine is administered (https://www.cdc.gov/vaccines/hcp/vis/current-vis.html). The VIS will be in the primary language of the parent(s) or legal guardian(s) consenting for the child to be enrolled in the study.
- An assessment of the number of influenza vaccine doses needed will be performed for children 5-8 years according to ACIP guidance. See FIG. 2, section 4.7.3.
- For children 5-8 years who are recommended to receive two doses of vaccine, study staff will document whether Dose #1 or Dose #2 will be given during the study. Additional guidance will be provided to the parent if Dose #2 is needed during the influenza season per section 4.7.3 below (*Seasonal Influenza Vaccine Single and 2-Dose Considerations for Participants aged 5-8 years*)
- The influenza vaccine will be administered according to the study randomization scheme.
- Documentation of influenza vaccine Dose #1 or Dose #2 will be provided to the parent(s) or legal guardian(s).
- Memory aid (daily symptom and peak flow diary on vaccination day, Day 1, and for the next 14 days, through Day 15, and on day 43) will be reviewed with the parent and the parent will demonstrate ability to take temperature and will be instructed in the collection of post-vaccination asthma clinical symptoms and symptom scores, adverse event, fever and concomitant medication administration data for 14 days (until day 15) after vaccination
- Parent(s) or legal guardian(s) will be given a thermometer to use for daily temperature recording
- Study staff will record any immediate adverse events (AEs) after vaccination occurring while still in the clinic. They will observe the child for at least 20 minutes after vaccination.

Study staff will instruct the parents/legal guardians to follow up with their child's healthcare provider if their child has a severe adverse event, worsening asthma symptoms or any other symptoms they find concerning

• Study staff will educate parents/legal guardians to notify the study staff if the patient requires an additional unscheduled medical visit for management of asthma symptoms (medical services utilization), has a severe adverse event, or a new asthma control medication that has been prescribed.

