4.3.6 Visit 6 (Day 43 + 7) – Contact [phone call(s), email(s), and/or text message(s)]

- Concomitant medications review
- Unsolicited symptoms review
- Medical services utilization review
- Obtain serious adverse event (SAE) information
- Post-vaccination asthma clinical symptoms review and symptom scores
 - Asthma control assessment (c-ACT/ACT, as appropriate by age)

Table 1: Schedule of Events

Study Visit	Enrollment Visit 1 (Vaccination)	Visit 2	Visit 3	Visit 4	Visit 5	Visit 6
Study Day	1	4	8	15	29	43
Visit Window (Days)	n/a	3-6	7-11	15-20	26-32	43-50
Type of Visit	In –person Clinic	Reminder only	Contact	Contact	Contact	Contact
Obtain Informed Consent through parental permission	X					
Obtain Assent (if applicable per site's IRB requirement)	Х					
Review Eligibility Criteria	Х					
Document Prior Year Flu Vaccination and present year influenza vaccine status for children 5-8 years	Х					
Review Medical History	Х					
May perform targeted physical exam	X					
Review Asthma History	X					
Assess asthma clinical symptoms ^a (PROSE)	X			X		
Assess asthma control ^b (c- ACT/ACT)	X					Х
Asthma severity classification ^c	Х					
Concomitant Medications ^d	Х		Х	Х	Х	Х
Urine or serum pregnancy test ^e	Х					
Oral temperature	Х					
Sex, Height, Weight, BMI	Х					
Peak Flow Measurement ^f	Х		Х	X		
Enrollment and Randomization ^g	Х					
Study Vaccination	Х					
Post vaccination evaluation period (at least 20 minutes)	X					
Distribute Memory Aid and other Materials	X					
Memory Aid Review (solicited symptoms)			Х	X		
SAE, unsolicited symptoms, and Medical Services Utilization ^h	X		Х	Х	Х	Х

^a Asthma clinical symptoms assessed using the PROSE questionnaire.

^b Asthma control assessed using the c-ACT or the ACT, as appropriate by age.

^c See section 4.4 in the protocol, for categories of asthma severity.

^d All current medications taken within 28 days prior to signing the informed consent form and through Day 43 (Visit 6).

^e Will be performed on all post-menarchal females within 24 hours before vaccination.

^fThe highest of 3 peak flow measurements will be recorded.

^g Participants will be randomized 1:1 to LAIV4 or IIV4; stratified by asthma severity and age stratum ^hMedical services utilization to include visits to doctor, urgent care, emergency room, hospitalization.

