8.2.2 Primary Outcome Measure

1. Proportions of asthma exacerbations in recipients of LAIV4 and IIV4 during the 42 days post-vaccination (until day 43).

The asthma exacerbation proportion within 42 days (until day 43) post-vaccination will be calculated for children receiving LAIV4 or IIV4 influenza vaccine. For this calculation a child with an asthma

exacerbation (as defined earlier in the protocol) on one or more days during day 1-43 would be considered to have had an asthma exacerbation (dichotomous yes or no). We propose a one-sided test for non-inferiority of asthma exacerbation in children receiving LAIV4 vs. children receiving IIV4. More precisely, we hope to reject the null hypothesis H0 indicating a higher proportion of children with asthma exacerbation (above an acceptable margin DELTA=10%) in the experimental (LAIV4) group as compared to the control (IIV4) group. Namely, PE is the true probability of event (asthma exacerbation) in the experimental group, PC is the true probability of event in the control group, and DELTA indicates maximum clinically acceptable absolute increase in the probability of event in the experimental group over probability of event in the control group. We hope to reject: H0: PE >= PC + DELTA in favor of alternative hypothesis H1: PE < PC + DELTA. The null hypothesis H0 will be rejected (and DELTA margin non-inferiority claimed) when the upper limit of the 95% one-sided confidence interval for the PE-PC is less than DELTA. More explicitly, if *pe* is the estimated event proportion in the experimental group; *pc* is the estimated event proportion in the control group; *ne* is the number of children in the experimental group; and *nc* if the number of children in the control group, then H0 is rejected if

$$\left((pe-pc)+z(0.95)\sqrt{\frac{pe(1-pe)}{ne}+\frac{pc(1-pc)}{nc}}\right) < DELTA$$

- 8.2.3 Secondary Objectives and Secondary Outcome Measures (SOM)
- 1. The first secondary objective (SO 1) is to compare the proportion of participants with asthma exacerbations during the 14 days (until day 15) after receipt of LAIV4 or IIV4.

Outcome measure: Comparison of the proportion of participants experiencing an asthma exacerbation during the 14 days after LAIV4 vs. IIV4.

The analysis is similar to primary objective 1 using a one-sided non-inferiority test with the alpha level set at 0.05 and non-inferiority margin of 10% though asthma exacerbation proportions during the 14 days post-vaccination is the outcome.

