3 STUDY OUTCOME MEASURES

3.1 Primary

POM 1.1: Proportion of participants with asthma exacerbations after LAIV4 vs. IIV4 during the 42 days after LAIV4 vs. IIV4 (Day 1 through Day 43)

Note: Asthma exacerbation is defined as: any acute episode of progressively worsening shortness of breath (dyspnea), cough, wheezing, chest tightness, and/or respiratory distress during the 42 days after influenza vaccination for which the patient seeks unscheduled medical attention (e.g., healthcare provider office or Emergency Department visit or hospitalization) or receives a new prescription for systemic corticosteroids.

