3.2 Secondary

SOM 1.1: Proportion of participants with asthma exacerbations during the 14 days after LAIV4 vs. IIV4

Note: For the purposes of this outcome measure, the above definition of asthma exacerbation (section 3.1) is modified to include the time period of 14 days after receipt of influenza vaccine (LAIV4 or IIV4)

SOM 2.1: Proportion of participants with asthma symptoms of cough during the 14 days after LAIV4 vs. IIV4

SOM 2.2: Proportion of participants with asthma symptoms of wheezing during the 14 days after LAIV4 vs. IIV4

SOM 2.3: Proportion of participants with asthma symptoms of tightness in chest during the 14 days after LAIV4 vs. IIV4

SOM 2.4: Proportion of participants with asthma symptoms of nighttime awakening during the 14 days after LAIV4 vs. IIV4

SOM 2.5: Proportion of participants with unscheduled albuterol use to treat asthma symptoms during the 14 days after LAIV4 vs. IIV4

SOM 3.1: Proportion of participants who experience a clinically significant decrease in peak flow measurement from baseline during the 14 days after LAIV4 vs. IIV4

Note: A clinically significant decrease in peak flow is defined as: a decrease of $\geq 20\%$ in PEFr from baseline PEFr.

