8.2 Secondary Objectives

There are three secondary objectives for this study.

- a) The first secondary objective (SO 1) is to compare the proportion of participants with asthma exacerbations during the 14 days after receipt of LAIV4 or IIV4.

The analysis is similar to primary objective 1 using a one-sided non-inferiority test with the alpha level set at 0.05 and non-inferiority margin of 10% though asthma exacerbation proportions during the 14 days post-vaccination is the outcome.

Asthma exacerbations will be assessed from day 1 through day 15. This information is captured on the memory aid forms and recorded in the REDCap database.

Definition of asthma exacerbation: *Any unscheduled medical attention (e.g., healthcare provider office, emergency department visit, hospitalization) due to any acute episode of progressively worsening shortness of breath/ dyspnea, cough, wheezing, chest tightness, and/or respiratory distress OR received a new prescription for systemic corticosteroids after LAIV4 vs. IIV4 during the 14 days post-vaccination will be counted as asthma exacerbations yes (1) and asthma exacerbations no (0) otherwise, for this analysis.*

SO 1 secondary objective will use one-sided ($\alpha=0.05$) non-inferiority test.

- b) The second secondary objective (SO 2) is to compare the proportion of participants with asthma symptoms and unscheduled albuterol use during the 14 days after receipt of LAIV4 or IIV4.

Proportions of subjects with each asthma symptom (yes or no) along with unscheduled albuterol use to treat asthma symptoms (yes or no) will be compared between two treatment groups using Chi-square tests. Proportions and difference of proportions between two treatment groups will be reported along with their 95% CIs.

The information regarding each symptom of cough, wheeze, tightness in chest, nighttime awakening and unscheduled albuterol use to treat asthma symptoms during Days 1-15 will be captured at home on the Memory Aid documents and solicited by study staff during phone calls or other communication methods. Data will be entered by study staff into the REDCap database.

SO 2 secondary objective will use the two-side ($\alpha=0.05$) superiority test

- c) The third secondary objective (SO 3) is to compare the proportion of participants who experience a clinically significant decrease in Peak Expiratory Flow Rate (PEFR) from baseline during the 14 days after receipt of LAIV4 or IIV4.

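### The SAP's yes/no scoring sentences for asthma exacerbation count any new systemic steroid prescription, while the endpoint definition counts only one given for an acute respiratory episode

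*SAP*

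**What the plan says.** The endpoint is defined in the outcome-measure sections. Protocol 2.2.1 starts from an acute episode of worsening respiratory symptoms "for which the patient seeks unscheduled medical attention" or receives a new systemic corticosteroid prescription. SAP 3.1 has the same structure: the episode is one "for which the patient seeks unscheduled medical attention (e.g., healthcare provider office or Emergency Department visit or hospitalization) or receives a new prescription", the drug prescribed being a systemic steroid. In both, the steroid limb sits inside the clause that begins with the episode.

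Two other places point back to that definition. Protocol 8.2.2 scores a child as having had an "exacerbation (as defined earlier in the protocol) on one or more days during day 1-43". SAP 3.2 says that, for the 14-day outcome, "the above definition of asthma exacerbation (section 3.1) is modified to include the time period of 14 days after receipt of influenza vaccine", so only the window changes.

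The scoring sentences in the SAP's analysis section are built differently. SAP 8.1 counts unscheduled medical attention due to an acute respiratory episode, and then adds "OR received a new prescription for systemic corticosteroids after LAIV4 vs. IIV4 during the 42 days post-vaccination". SAP 8.2, under the first secondary objective, adds "OR received a new prescription for systemic corticosteroids after LAIV4 vs. IIV4 during the 14 days post-vaccination" and labels its sentence as the definition of asthma exacerbation. Both end by assigning 1 for yes and 0 otherwise.

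**The concern.** In SAP 8.1 and 8.2 the phrase that requires an acute episode qualifies medical attention only. The capitalised OR makes the steroid prescription a sufficient condition by itself, with no indication attached. A child given a steroid course for a rash, say, with no respiratory symptoms, would score 1 under these sentences and 0 under SAP 3.1.

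These sentences give the SAP's explicit 1/0 coding for the primary endpoint and for the only other non-inferiority test, so an analysis programmer may well work from them. If unrelated courses are equally common in both arms, counting them adds noise, which lowers power. It also slightly shrinks any true excess after LAIV4, which in a non-inferiority comparison favours the claim of non-inferiority.

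**Working it through.** **1. Wording, side by side.**

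| Place | Medical-attention limb needs an acute respiratory episode? | Steroid limb needs one? |
|---|---|---|
| Protocol 2.2.1 | Yes | Yes |
| SAP 3.1 (and 3.2, which changes the window only) | Yes | Yes |
| Protocol 8.2.2 | Yes, by reference back | Yes, by reference back |
| SAP 8.1 (42 days) | Yes | Not stated |
| SAP 8.2, first secondary objective (14 days) | Yes | Not stated |

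No order of precedence is stated. The first three rows are the outcome definitions and the passages that refer to them, so they are the natural reading of what is meant.

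**2. Could an unrelated steroid course reach the data?** Several capture instructions are asthma-specific (parts of Protocol 4.3, and 4.8 to 4.10). The memory aid, which SAP 8.1 names as the source, also takes "concomitant medication administration data for 14 days (until day 15) after vaccination" (Protocol 4.3.1). Table 1, note d, collects all current medications through Day 43. The route is narrow but open.

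**3. The plan's own power figure.** Inputs from Protocol 8.1 and SAP 4.2: 12% in each arm, 135 per arm, margin 10 points, one-sided alpha 5%. The rejection rule is the unstratified one in Protocol 8.2.2.

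- SE = sqrt(2 × 0.12 × 0.88 / 135) = 0.03955
- Power = Φ(0.10 / 0.03955 − 1.645) = 81.1%, as stated in the plan.

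**4. Effect of the literal rule (conditional).** Let e be the share of children otherwise without an event who have an unrelated steroid course, equal in both arms. The documents give no value, so 0 to 3% is an assumption. It is also assumed that the planning 12% is the rate under the strict definition.

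- With no true difference: scored risk p = 0.12 + 0.88e; power = Φ(0.10 / sqrt(2p(1 − p)/135) − 1.645); extra events = 270 × 0.88 × e.
- With a true 22% versus 12%: scored risks 0.22 + 0.78e and 0.12 + 0.88e, so the scored excess is 0.10 × (1 − e). The chance of declaring non-inferiority comes from the same rule.

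| e | p | Extra events | Power | Scored excess (points) | False non-inferiority |
|---|---|---|---|---|---|
| 0 | 12.0% | 0 | 81.1% | 10.0 | 5.0% |
| 0.5% | 12.4% | 1.2 | 80.1% | 9.95 | 5.1% |
| 1% | 12.9% | 2.4 | 79.0% | 9.9 | 5.2% |
| 2% | 13.8% | 4.8 | 77.0% | 9.8 | 5.5% |
| 3% | 14.6% | 7.1 | 75.2% | 9.7 | 5.7% |

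Exact binomial enumeration of the same rule agrees. From e = 0 to e = 3%, power goes from 81.2% to 75.3%, and false non-inferiority from 5.2% to 5.9%.

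**The case against.** The strongest reply is that the rest of the plan already settles the matter. SAP 3.1 gives the full definition, SAP 3.2 and Protocol 8.2.2 refer back, and the scoring sentence stands in a paragraph about asthma exacerbations. The sentence is also grammatically incomplete: its second limb has no subject, so a reader may go back to SAP 3.1 to supply one. This shows what was probably intended, and the point is best treated as a drafting slip. It does not remove two scoring rules whose wording departs from the definition.

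A second reply is that the memory aid, the case report form and the manual of procedures named in SAP 5.1 are not in the file. The steroid field may already be restricted to asthma, or may record a reason, and nothing says that the general medication list feeds the endpoint. That is fair. It means that an actual effect on the endpoint cannot be shown from the documents, only that the text permits one.

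A third reply is that the trial is open label, so linking each prescription to an episode adds a judgement made with knowledge of the vaccine. That caution stands as a reason to set the rule in advance. The strict definition already requires the link, however, and so does the medical-attention limb in SAP 8.1 itself.

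**Conclusion.** The concern holds, as a minor one. The wording difference is certain: read literally, SAP 8.1 and 8.2 score events that Protocol 2.2.1 and SAP 3.1 exclude. The size is conditional. With no unrelated steroid courses, or with a case report form that already filters them, there is no effect. At up to 3%, equal in both arms, the loss is at most about 6 points of power, and false non-inferiority rises by at most about 0.7 points. If the 12% planning rate already includes such courses, power stays at the planned 81.1% and the figures above overstate the loss.

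**What to change.** Replace the scoring sentences in SAP 8.1 and in SAP 8.2 (first secondary objective) with the SAP 3.1 definition. Score 1 if it is met from Day 1 through Day 43, or through Day 15 with the 14-day window for the secondary objective, and 0 otherwise.

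Alternatively, keep the sentences and add one line: *A new systemic corticosteroid prescription counts only when it is for a qualifying acute episode as defined in SAP 3.1.*

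It would also help to state in advance how a prescription with no recorded reason is scored, with the opposite scoring as a sensitivity analysis. Since the trial is open label, fixing this beforehand limits case-by-case judgement.

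The cost is two SAP sentences and a small programming change. The reason for some steroid prescriptions will have to be checked in data already collected. The 12% planning rate, 135 per arm and 81.1% power stand unchanged.

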7.1 Handling of Withdrawals

Participants who withdraw from the study before randomization will be replaced. Participants who withdraw from the study after randomization will not be replaced. Every attempt should be made to collect all data specified by the protocol relative to study vaccine received up to the time of withdrawal. Data collected before withdrawal will still be used for analysis.

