4.2 Sample Size and Power

This study aims to enroll approximately 300 participants (approximately 100 from Vanderbilt, approximately 110 from Cincinnati, and approximately 90 from Duke). We assume that the proportion of participants with asthma exacerbation(s) in 42 days after vaccination is 12% after LAIV4 and IIV4 [1]. We also assume that ~10% of the children may drop out, yielding a total sample of at least 270 (135 LAIV4 and 135 IIV4).

Our research hypothesis is that the proportion of participants with asthma exacerbation(s) in the LAIV4 (experimental group) will not be higher than in the IIV4 group (control group). The power estimate is shown below, given delta of 10% and one-sided alpha is set at 5% level.

Proportion of participants with asthma exacerbation(s) in control IIV4 group (pc)	Proportion of participants asthma exacerbation(s) in LAIV4 experimental group (pe)	Estimated power to reject H0: pe – pc >= 10%
---	--	---

12%	12%	81.1%
-----	-----	-------

The null hypothesis is that the proportion of participants with asthma exacerbation(s) in the LAIV4 group will be inferior (higher) than the proportion in the IIV4 group. The null hypothesis will be rejected (and delta margin noninferiority claimed) when the upper bound of the 95% one-sided confidence interval for the pe minus pc is less than 10%. IBM SPSS SamplePower software version 3.0.1 was used for the power calculation which was not adjusted for stratifying by site.

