6 ANALYSIS POPULATIONS

6.1 Intent-to-Treat (ITT) Population:

The ITT Population includes any participant that was enrolled, randomized into the study, and received a study vaccine at Visit 1.

6.2 Per Protocol Population for 43 Days:

The Per Protocol Population for 43 days (PP43) is a subset of the ITT Population. This is defined as all participants who were randomized, vaccinated, completed study procedures

through day 43, had no protocol deviations that are likely to affect the objectives, and did not receive a second dose of influenza vaccine before day 43.

6.3 Per Protocol Population for 15 Days:

The Per Protocol Population for 15 days (PP15) is a subset of the ITT Population. This is defined as all participants who were randomized, vaccinated, completed study procedures through day 15, had no protocol deviations that are likely to affect the objectives, and did not receive a second dose of influenza vaccine before day 15.

The Per Protocol Population for 43 days is the primary analysis population for the Primary Objective. Statistical analyses for the Primary Objective will be performed for the ITT population and the Per Protocol for 43 days, or the ITT Population only if no participants are excluded from the Per Protocol Population. The Per Protocol population for 15 days is the primary analysis population for the Secondary Objectives. Statistical analyses for the Secondary Objectives will be performed for the ITT population and Per Protocol population for 15 days, or the ITT Population only if no participants are excluded from the Per Protocol Population. The list of protocol deviations that meet criteria for exclusion from analysis is provided in Appendix 2.

In the ITT population, participants will be analyzed according to randomization assignment, rather than treatment group. If applicable, sensitivity analyses on primary and secondary objectives will be done on datasets defined by treatment group. For example, if a participant was assigned to LAIV4 and inadvertently received IIV4 that participant would be reassigned to the IIV4 treatment group in the sensitivity analyses.

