10 SENSITIVITY ANALYSES

If applicable, sensitivity analyses on primary and secondary objectives will be done on datasets defined by treatment group. If applicable, sensitivity analyses on primary and secondary objectives will be done on datasets defined by treatment group. For example, if a participant was assigned to LAIV4 and inadvertently received IIV4 that participant would be reassigned to the IIV4 treatment group in the sensitivity analyses.

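### The SAP codes the exacerbation outcome 0 unless an event is recorded and has no missing-outcome rule, so a child lost early counts as event-free in the supporting ITT analysis

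*SAP*

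**What the plan says.** SAP 8.1 scores the primary outcome 1 for a qualifying exacerbation and 0 in every other case: an event "during the 42 days post-vaccination will be counted as asthma exacerbations yes (1) and asthma exacerbations no (0) otherwise, for this analysis". SAP 8.2 uses the same form for the first secondary objective (SO 1): "during the 14 days post-vaccination will be counted as asthma exacerbations yes (1) and asthma exacerbations no (0) otherwise, for this analysis".

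SAP 6.1 sets no follow-up requirement for ITT: "The ITT Population includes any participant that was enrolled, randomized into the study, and received a study vaccine at Visit 1". SAP 6.2 requires completed study procedures through day 43 for the per-protocol population (PP43). On their roles, SAP 6 says: "The Per Protocol Population for 43 days is the primary analysis population for the Primary Objective". The primary objective is also analysed in ITT.

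On loss, SAP 4.2 says "We also assume that ~10% of the children may drop out" and gives no split by arm and no timing. Protocol 7.1 does not replace children who withdraw after randomization, and adds: "Data collected before withdrawal will still be used for analysis". It does not say how the unobserved remainder is scored.

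Two other places come near the question. SAP 7.2 is descriptive: "The number of visits completed and missed will be presented along with the completeness of memory aid". SAP 10 covers only the vaccine actually received: "If applicable, sensitivity analyses on primary and secondary objectives will be done on datasets defined by treatment group".

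**The concern.** ITT is the only planned analysis that keeps children who did not finish follow-up. If it counts them as event-free, neither analysis tests whether exacerbations are hidden among the losses: PP43 drops these children and ITT assumes that they did well.

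In a non-inferiority comparison of a safety outcome, that assumption is not conservative. If a fraction d of each arm is lost and only part of the window is seen, both risks shrink by the same factor, and so does the difference between them. An ITT bound below 10 points beside a PP43 bound below 10 points then looks like independent confirmation, although part of the agreement comes from the coding. If loss differs between the arms, which is possible in an open-label trial, the coded difference can move in either direction.

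**Working it through.** **Inputs from the documents.** 12% risk in each arm, a 10-point margin, one-sided alpha of 0.05, about 300 enrolled (150 per arm), about 10% dropout, 135 evaluable per arm (SAP 4.2). Decision rule from Protocol 8.2.2: reject H0 if (pe − pc) + 1.645·√[pe(1−pe)/ne + pc(1−pc)/nc] < 0.10.

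**Assumptions.** The timing of loss and its split by arm are not given. f is the share of the event risk in the window that is observed, on average, in a lost child.

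**The plan's own figure.** With 135 per arm and 12% in both arms, SE = √(2 × 0.12 × 0.88 / 135) = 0.0396. Power = Φ(0.10/0.0396 − 1.645) = Φ(0.883) = 81.1%, as stated. It rests on 135 evaluable children per arm, so the coding of lost children does not enter.

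**ITT with lost children coded 0, equal loss.** The coded risk is p × [1 − d(1 − f)]. At the null boundary (22% vs 12%) with d = 0.10 and f = 0.5, the factor is 1 − 0.10 × 0.5 = 0.95. The coded risks are 20.9% and 11.4%, a difference of 9.5 points.

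The table gives the chance that the rule is met, by exact binomial enumeration, unstratified, with 150 per arm unless noted.

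| Loss per arm | Share observed, f | Coded difference (points) | Rule met |
|---|---|---|---|
| None | – | 10.0 | 5.3% |
| 5% | 0.5 | 9.75 | 6.0% |
| 10% | 0.5 | 9.5 | 6.7% |
| 10% | 0.36 | 9.4 | 7.2% |
| 10% | 0 (extreme) | 9.0 | 8.5% |
| PP43, 135 per arm | complete | 10.0 | 5.2% |

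The value 0.36 assumes that loss is spread evenly over 42 days and that events are known only up to the last completed contact (day 8, 15 or 29): (7×0 + 7×7 + 14×14 + 14×28)/42 = 15.2 days, and 15.2/42 = 0.36.

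**Unequal loss, f = 0.5.**
- 15% lost in LAIV4 and 5% in IIV4: 22% × 0.925 − 12% × 0.975 = 20.35% − 11.7% = 8.65 points. Rule met 9.8% of the time (9.7% in a site-stratified simulation).
- 5% and 15%: 22% × 0.975 − 12% × 0.925 = 21.45% − 11.1% = 10.35 points. Rule met 4.5% of the time.

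**Both analyses passing.** In site-stratified simulations of 200,000 trials at 22% vs 12%, PP43 and zero-coded ITT both pass 4.6% to 4.8% of the time with 10% loss in each arm, 5.1% with 15%/5% and 3.9% with 5%/15%.

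**Example.** Take 20 (LAIV4) and 16 (IIV4) events among 135 completers per arm, with 15 lost per arm and no event recorded among them.
- PP43, 20/135 vs 16/135: difference 2.96 points, upper bound 9.8.
- Zero-coded ITT, 20/150 vs 16/150: difference 2.67 points, upper bound 8.8. The bound falls by almost a point with no new information.
- Lost IIV4 children at the observed IIV4 risk: 16 + 15 × 16/135 = 17.8 events. If 3 of the 15 lost LAIV4 children had an event (23 vs 17.8 of 150), the bound is 9.98. If 4 did (24 vs 17.8), it is 10.7.

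**SO 1.** Assume that the 14-day risk is proportional (12% × 14/42 = 4%), with 14% vs 4% at the margin, 3.3% lost by day 15 (10% × 14/42) and f = 0.5. The factor is 0.9835, the coded difference is 9.8 points, and the rule is met 6.4% of the time instead of 5.8%. With an IIV4 risk of 2% the change is from 6.4% to 7.1%, and with 6% it is from 5.5% to 6.1%.

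**The case against.** The strongest reply is that nothing is decided on ITT. PP43 is primary, and the rejection rule does not require ITT to pass. That stands. A reader might infer that zero-coding inflates the type I error of the non-inferiority claim. The documents do not support this: children lost before day 43 are not in PP43, its rate stays at 5.2%, and even a requirement that both analyses pass gives at most 5.1% in the scenarios above. The provision to use ITT alone changes nothing, because it applies only when PP43 excludes no one, and then no child has been lost.

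A second reply is that the 0 category merely completes an event definition and was never meant as a rule for missing data. An analyst could set lost children to missing. That is fair: the SAP does not say outright that missing equals 0. But no other rule exists, so the literal reading is the only one written down.

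A third reply is that the larger figures need conditions the documents do not suggest, such as threefold higher loss in LAIV4 or no follow-up at all in lost children, and that the example starts close to the margin. This also stands. Those figures show direction and range; they are not forecasts.

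A fourth reply is that parents are told to call staff about unscheduled asthma visits (Protocol 4.3 and 4.9), so events may be known after the last scheduled contact. That reduces the zero-coding bias and also limits one remedy, Kaplan-Meier with censoring at last contact. In simulations with 10% loss and a true 10-point difference, zero-coding gives about 9.3 to 9.4 points and Kaplan-Meier 10.0 if no later events are reported. If all are reported, the values are about 9.9 to 10.0 and 10.4 to 10.5. Kaplan-Meier should therefore be an option and not a requirement.

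**Conclusion.** The point holds as a gap in the supporting ITT analysis. As written, the rule counts a lost child with no recorded event as event-free, and no other part of either document handles the unobserved outcome.

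With equal loss the effect is modest: 10 points becomes about 9.5, and ITT alone meets the margin 6.7% instead of 5.3% of the time at 22% vs 12%. This assumes 10% loss in each arm and half the window observed. Unequal loss can make the effect larger or reverse it. Loss timing, loss by arm and the 14-day risks are assumptions; the documents give only the overall dropout of about 10%.

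The primary analysis, its error rate, its power and the decision rule are untouched. The issue is how much a passing ITT result says about the children who were lost. The change should be made, because it is cheap and ITT is the only planned analysis that includes these children.

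**What to change.** In SAP 8.1 and 8.2, state for ITT: score 1 for any qualifying event recorded; score 0 only when follow-up for events reaches day 43 (day 15 for SO 1); treat every other child as unobserved, not event-free.

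Add one tipping-point analysis to SAP 10. Hold lost IIV4 children at the observed IIV4 risk, raise the assumed risk in lost LAIV4 children until the one-sided 95% upper bound reaches 10 points, and report that risk. In the example above, the tipping point lies between 3 and 4 events among the 15 lost LAIV4 children.

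Name the ITT estimator as well. Simply dropping the unobserved children while keeping events seen before loss is not neutral. At 10% loss and half the window it gives 0.209/(0.90 + 0.10×0.5×0.22) − 0.114/(0.90 + 0.10×0.5×0.12) = 22.9% − 12.6%, or about 10.4 points for a true 10. Site-stratified Kaplan-Meier is one acceptable choice if event and last-contact dates are recorded. With no loss it equals the Mantel-Haenszel difference when both use Mantel-Haenszel site weights. It assumes that loss is unrelated to outcome, and it overstates the difference by up to about 0.5 points if events are reported after the last scheduled contact while event-free children are censored there.

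Leave PP43, its Cochran-Mantel-Haenszel analysis, the margin and the decision rule as they are.

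The cost is a few sentences, a little more programming and a slightly wider ITT interval. With Kaplan-Meier, the one-sided half-width at 22% vs 12% grows from 6.9 to 7.2 points, and ITT power at 12% vs 12% is about 83% instead of about 86% under zero-coding. The daily diary ends at day 15, so the sponsor should confirm that event dates after day 15 are captured before choosing a time-to-event estimator.
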